#### 7.2.2 Approach for comparisons across intervention arms

*CDS analyses:* We will test whether each outcome differs as a function of each CDS active arm (CDS-OS and CDS-MTDM) relative to no-CDS control. Regressions will include as covariates education arm and interactions between CDS and education. We will retain both terms if the interaction is significant and retain the main effect if only it is significant. The education variable in CDS analyses will be coded as delayed education (baseline), early education, other (for clinicians who were not in the system early enough to be included in an education arm, to avoid either diluting or biasing the education effects).

As an exploratory analysis, we will compare CDS-MTDM against CDS-OS to see which is most effective.

Additionally, covariates will be added to exploratory versions of the final models as sensitivity analyses, to adjust for measured differences across clinicians, such as role, number of patients seen, and baseline rates of prescribing each of the GDMT classes. We have no *a priori* hypotheses about the moderating effects of these covariates.

*Education analyses:* We will test whether each outcome differs as a function of early education relative to delayed education. Regressions will include as covariates CDS arm and interactions between CDS and education. We will retain both terms if the interaction is significant and retain the main effect if only it is significant. Assignment to early versus delayed education is not random; therefore, regression analysis comparing education to no-education controls will adjust for as many relevant covariates as possible, including baseline prescribing rates.

In these analyses, we will exclude clinicians who were not present throughout the data collection period, beginning at assignment to early education. That is, we only intend to include clinicians in early and delayed education arms who theoretically could have been exposed to the education and who then had time to treat patients based on what they learned.

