- Interventions – We will implement the following interventions: 1) focused education through a series of focused in-person or virtual sessions (randomized to receive early or late education); 2) multi-pronged clinical decision support (CDS) inclusive of a patient portal message, an interruptive advisory upon chart entry notifying clinicians to consider GDMT, and a Best Practice Advisory (BPA) that opens a GDMT order set; and 3) the same CDS as #2 but replacing the GDMT order set with a referral to integrated clinical pharmacist co-management.
- Control – Patients seen by clinicians randomized to usual care will be labeled as control patients and receive care as per usual standard practice, which may also include referral to Medication Therapy Disease Management (MTDM).

- Outcomes – The primary outcome will be whether or not improvements in GDMT prescribing occur within 30 days of index date. Additional outcomes will include the primary outcome at 60 and 90 days, GDMT changes at 30, 60 and 90 days, healthcare resource utilization, and total costs of care.
- Data analysis – Analyses are described in detail below. Primary analyses will assess whether outcomes improve between each interventional arm versus control.

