### 5.2 Hypothesis

$H_0$ : The implementation of a multifaceted, interdisciplinary intervention will not improve GDMT for patients with HFrEF.

$H_{A1}$ : The implementation of a multifaceted, interdisciplinary intervention incorporating an order set will improve GDMT for patients with HFrEF more than usual care.

$H_{A2}$ : The implementation of a multifaceted, interdisciplinary intervention incorporating a pharmacist referral will improve GDMT for patients with HFrEF more than usual care.

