## 6. STUDY METHODS

### 6.1 Study Design

This is a cluster randomized study designed to evaluate the effectiveness of interventions aimed at improving GDMT in patients with HFrEF. Clinicians were stratified based on practice specialty, location, and pharmacist referral habits (see details below) and were permuted block randomized to achieve 45%/45%/10% proportional distribution across the following arms respectively: (1) usual care (**Control arm**); (2) multi-pronged CDS inclusive of a patient portal message about GDMT, an interruptive advisory upon chart entry advising clinicians of the need to optimize treatment, and a BPA that links to a GDMT order set

(**CDS-OS arm**); and (3) multi-pronged CDS as in #2 but replacing GDMT order set with referral to integrated clinical pharmacist co-management (**CDS-MTDM arm**). Secondarily, each of the 5 clinical practice sites of roughly equal HFrEF patient loads were assigned to receive either an early or delayed education rollout.

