The target audience for this education program are Cardiology clinicians (physicians (MD, DO) and advanced practitioners (PA, CRNP)) at Geisinger. Three clinics were selected for early education (i.e. before additional CDS and pharmacist referral interventions) and two clinics were reserved for late education (timed to occur after sufficient time has elapsed to assess the impact of the early education on its own). The early education programs were delivered over one month to each clinic with in-person attendance being encouraged.

Topics delivered in the early education sessions included:

1. Sacubitril / Valsartan (ARNI) in CHF
2. SGLT2 inhibitors in CHF
  - a. SGLT2i in Cardiovascular Disease & HFrEF
  - b. SGLT2i in HFrEF with Diabetes: What the Cardiologist should know
3. Management of HFrEF and chronic kidney disease (CKD)
4. Geisinger Pharmacist role in HFrEF

The early education sessions were delivered live, at each clinic location separately on a given date (either in-person or virtually depending on clinic preference).

Participants were encouraged by the lead PI to attend the live sessions if they were being offered at their clinic location. Continuing medical education (CME) credits were provided to attendees where applicable and lunch was provided during the live sessions. Presentations lasted about 30 minutes with a question-and-answer session to follow. An RSVP request was asked of those attending. Those missing their sessions were invited to a virtual session being held to try to increase attendance rates. The virtual sessions were recorded. The same approach will be used for delayed education.

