## 7. STATISTICAL ANALYSIS PLAN

### 7.1 Power analysis

Data will be collected from 4,300 patients assigned to the clinicians in the study. With CDS-OS and CDS-MTDM (versus control), we expect to have 80% power to detect approximately 5 and 9 percentage-point increases, respectively, in prescribing GDMT within 30 days, at two-tailed  $p < .05$  with robust standard errors clustered at the clinician level. With education versus delayed education, we expect to have 80% power to detect an approximately 5.5 percentage-point increase in prescribing GDMT, with robust standard errors clustered at the clinician level. Power analyses were conducted using DeclareDesign.

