## **10. PROJECT STATUS**

Early education was launched on 8/1/2023 and data collection is ongoing. CDS and MTDM arms launched on 10/9/2023. Outcome data have not yet been extracted or examined as a function of study arms, except in a very limited way for the initial BPA investigation described below.

We removed non-telemedicine telephonic encounters as an inclusion criterion partway into data collection (as of 11/4/2023), based on immediate post-launch investigations of BPAs that were intended to help ensure BPAs were functioning correctly and firing appropriately in terms of patients, clinicians, and encounters. These investigations included chart reviews to examine acknowledgement reasons and prescribing patterns in the referral and order set arms. The results suggested that telephonic encounters were inappropriate occasions in which to expect clinicians to make prescription adjustments, given other pressing reasons for a majority of these calls (e.g., review of lab results, scheduling appointments) and very low rates of prescribing during these encounters. Prescribing rates were not compared between the no-BPA control arm and the CDS arms, and no other outcomes were examined.

Telemedicine telephonic encounters remain a valid inclusion criterion, as those are scheduled appointments appropriate for prescribing.

Within the referral arm only, data on referral rates across clinicians were monitored and chart reviews conducted to better understand where and why referrals to MTDM were not occurring for certain clinicians. These data were used to inform follow-up by MTDM pharmacists and potential escalation by clinical leadership to overcome lack of awareness and educate clinicians on the purpose and appropriate use of the referral. For example, if referral rate to MTDM for a given clinician was below 50% in February 2024, the study PI contacted the clinicians to educate or remind them about the benefits of pharmacy co-management.

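### A significance test of the CDS-by-education interaction decides what the primary CDS result estimates, and no overall contrast is named if the interaction is kept

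*Combined protocol and SAP*

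**What the plan says.** The abstract (Section 3) states the target: "Primary analyses will assess whether outcomes improve between each interventional arm versus control". Both alternative hypotheses in Section 5.2 have the same form, that a CDS intervention "will improve GDMT for patients with HFrEF more than usual care". Neither is limited to an education group.

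Section 7.2.2 (CDS analyses) sets the model: "Regressions will include as covariates education arm and interactions between CDS and education. We will retain both terms if the interaction is significant". If only the main effect is significant, that term alone is kept. On coding: "The education variable in CDS analyses will be coded as delayed education (baseline), early education, other". The third level holds clinicians who arrived too late to be in an education arm.

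Section 6.1 describes "each of the 5 clinical practice sites of roughly equal HFrEF patient loads" as the units assigned to early or delayed education. Section 6.7 (Focused Education) gives the split as three early clinics, and "two clinics were reserved for late education". Section 7.2.2 says this assignment was not random.

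Section 7.1 claims "80% power to detect approximately 5 and 9 percentage-point increases, respectively" for CDS-OS and CDS-MTDM against control, with 4,300 patients, two-sided 5% tests and clinician-clustered standard errors.

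**The concern.** Three things are left to the data or to the analyst.

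- **The estimand.** Without the interaction, the CDS coefficient is an effect across all education levels. With it, and delayed education as reference, the coefficient is the effect among clinicians coded delayed. An overall effect can be computed from the larger model, but the plan gives no contrast or weights for it.
- **The test.** Two CDS arms and two non-reference education levels give 2 × 2 = 4 product terms. A joint test and a term-by-term check have different chances of keeping the interaction.
- **Consistency.** The rule applies to each outcome separately, so the 30-day primary and the 60- and 90-day secondary outcomes could be reported from different models, with coefficients that mean different things.

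The delayed group is also not a clean reference. Section 10 says delayed education began in August 2024 with enrolment incomplete. It restricts the primary education analysis to earlier encounters but states no such limit for the CDS analysis.

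At stake are the error rate and power of the primary test and, above all, whether the reported number answers the question in Section 5.2.

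**Working it through.** **1. The plan's power figure.** Section 7.1 gives neither a control rate nor an intraclass correlation, so the figure cannot be reproduced exactly. With 45/45/10 of 4,300 patients (1,935 / 1,935 / 430), 5 points at 80% power fits a design effect of 2.82, 1.55 or 1.24 for assumed control rates of 10%, 25% or 50%. The same design effects give 8.3 to 8.4 points for CDS-MTDM, near the stated 9. The power statement is therefore plausible for one overall effect per arm, and I calibrate to it.

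**2. Standard errors.** For 80% power at two-sided 5%, effect / SE = 1.960 + 0.842 = 2.802.
- CDS-OS: SE = 5 / 2.802 = 1.78 points
- CDS-MTDM: SE = 9 / 2.802 = 3.21 points

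**3. The delayed-group coefficient.** With equal CDS allocation in every education level and delayed share p, its SE is the overall SE divided by √p. Two of five sites of similar load give p = 0.40.
- SE ratio: 1 / √0.40 = 1.58
- Detectable at 80% power: 5 / √0.40 = 7.9 points and 9 / √0.40 = 14.2 points
- Power at 5 (or 9) points: Φ(2.802 × √0.40 − 1.960) = Φ(−0.188) = 42.5%

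Counting the 'other' level lowers p. If it holds 10% of patients (assumed), p = 0.36 and the detectable effects are 5 / 0.6 = 8.3 and 9 / 0.6 = 15.0 points.

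**4. The two-stage rule, same CDS effect everywhere.** Normal-theory simulation with a shared control arm. If the interaction is significant at 5%, test the delayed-level coefficient; otherwise test the additive-model coefficient. 'Joint' is a chi-square test on all product terms; 'any term' means any |z| > 1.96. Three education levels match the plan's coding; the share in 'other' is an assumption.

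| | Two levels: joint / any term | Three levels, 'other' 10–20%: joint / any term | Fixed main-effects model |
|---|---|---|---|
| Interaction kept by chance | 5.0% / 9.5% | 5.0% / 17–18% | not applicable |
| Type I error per arm | 6.2% / 6.8% | 5.8–5.9% / 6.9–7.1% | 5.0% |
| Power at 5 and 9 points | 78% / 77% | 78% / 73–74% | 80% |
| False significance when kept | 28–29% / 23% | 21–22% / 16–18% | 5% in the same trials |

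In the two-level case with true effects of 5 and 9, power among trials that keep the interaction is about 47% / 46–47%; the fixed model has 80% in those same trials.

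A separate calculation, assuming a 25% control rate, intraclass correlations of 0.01 to 0.025 and up to a third of clinicians in 'other', gave type I error of 5.7 to 6.3% (joint) and 6.7 to 7.6% (any term).

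**5. The rule when effects differ.** The documents give no size or direction for an interaction, so these cases are illustrations: two levels, p = 0.40, overall effects held at 5 and 9.

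| CDS-OS effect, delayed / early | Check | Kept: joint / any term | Power: joint / any term | Mean kept CDS-OS coefficient |
|---|---|---|---|---|
| 2.5 / 6.67 | 0.4 × 2.5 + 0.6 × 6.67 = 5.0 | 23% / 35% | 63% / 54% | 0.4 / 0.9 |
| 7.5 / 3.33 | 0.4 × 7.5 + 0.6 × 3.33 = 5.0 | 23% / 35% | 83% / 84% | 9.6 / 9.2 |

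CDS-MTDM effects were scaled alike (4.5 / 12 and 13.5 / 6). The last column covers only trials that keep the interaction. The fixed model has 80% power in both rows.

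**6. Cell size.** CDS-MTDM has about 10% of 103 to 155 clinicians. At a 40% delayed share, its delayed cell holds 0.10 × 103 × 0.40 = 4.1 to 0.10 × 155 × 0.40 = 6.2 clinicians, too few for reliable cluster-robust standard errors.

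**The case against.** The plan does not say that the printed reference-level coefficient would be the primary result. An analyst could average over education levels, and the arms are described as crossed with education, so looking at the interaction is reasonable. The retention rule is itself written in advance. With a common CDS effect the damage is small, and the kept coefficient is noisy but not biased. The large distortions need interactions that no document supports. The simulation also skips one step of the rule, dropping a non-significant education main effect, and uses ideal standard errors.

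Much of this stands as a limit on the figures. They assume that the coefficient as coded is read as the CDS effect, the three-level conditional error rates are lower than the two-level ones, and the heterogeneous cases are illustrations only. That Section 7.1's power refers to an overall effect is an inference, since the simulated model is not described. What does not stand is the defence that the rule is prespecified. The selection step is; the quantity reported after it and the form of the interaction test are not. Averaging later would mean choosing the contrast and its weights with the data in hand.

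**Conclusion.** The concern holds and should be fixed. A preliminary p-value decides whether the primary CDS coefficient is an overall effect or an effect among clinicians coded delayed, and the plan names neither an averaged contrast nor the form of the test.

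With a common effect the loss is modest: 0.8 to 2.1 points of type I error and 2 to 7 points of power under the plan's three-level coding. With a real interaction the reported coefficient can be far from the overall effect in either direction, by about 4 to 5 points around an overall effect of 5 in the two examples, when the interaction is kept.

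These sizes rest on standard errors calibrated to Section 7.1, equal CDS allocation across education levels, a 60/40 early/delayed split, and an assumed 10 to 20% in 'other'. The gap in the text depends on none of these.

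**What to change.** Name one primary CDS model in Section 7.2.2: indicators for CDS-OS and CDS-MTDM plus the three-level education variable as a main effect, kept whatever its p-value, with no retention of terms by significance. Alternatively, centre the education indicators at their sample means, so that the CDS coefficients are averages over the enrolled patients even with the interaction in the model.

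Report the CDS-by-education interaction as a secondary analysis for each outcome, with one joint test on all four product terms and the CDS effect with its confidence interval in each education group.

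The cost is SAP wording. Section 10 says "Outcome data have not yet been extracted or examined as a function of study arms", apart from a limited check of how the alerts fired, so as of this version the choice can still be made without knowledge of results. Under a common effect the fixed model gives 5% error and 80% power on the assumptions above. If the effect is larger in the delayed group it gives up a few points of power (80% against 83 to 84% in the example).

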## 6.2 Randomization details

Permuted blocked randomization was completed once at the beginning of the study.

Randomization was stratified as described below given concerns about imbalances in GDMT prescribing practices across clinics, certain roles, and current MTDM referral practices.

Clinicians were divided into HF specialists and non-HF specialists given differences in practicing patterns and propensity for increased GDMT prescribing patterns among specialists.

Within Non-HF specialists, randomization was stratified on the following variables:

- Role: electrophysiology, interventional, non-invasive
- MTDM referral history: none/0%, 1%-100%
- Primary practice location: Northeast (GCMC, GWV, Orwigsburg), Central (GMC, Shamokin, Lewisburg), and West (GLH, Gray's Woods)

Within HF specialists, randomization was stratified on MTDM referral history. They were NOT stratified on practice location because there was not hypothesized to be a significant difference in practice as a function of location in this group.

We also generated permuted block randomized sequences for allocating any new clinicians who enter the system during the study. The study team collected information about role and primary practice location for any new clinician joining the system monthly. However, all new clinicians were assigned to the 0% MTDM referral history stratum, because new clinicians do not have an MTDM referral history in the system. Based on the pre-randomized sequence generated, the clinician would be assigned to an interventional arm. In generating these sequences, we assumed turnover rates would be equal across strata.

One hundred and fifty-five clinicians (103 current and 52 hypothetical) were randomized into control (45%), CDS-OS (45%) and CDS-MTDM arms (10%).

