### 7.2.3 Regression Specifications

For all outcomes except timing of GDMT increases and ROI outcomes, ordinary least squares (OLS) regressions will be run with heteroskedasticity-robust standard errors clustered at the clinician level (to account for clustering of patients within clinicians). We will also explore the effect of clustering standard errors at the clinic level.

We will run a survival analysis to assess timing of GDMT increases.

Cost and outcomes estimate for the cost-effectiveness model will be obtained using EHR data, claims data, and literature-based sources. These data will be used to develop a decision tree analytical model with a state transition Markov cohort simulation to compute incremental cost effectiveness ratios (ICER), cost-effectiveness acceptance curves will be generated for all cost-effectiveness measurements. The effects of uncertainties from the model parameters will be evaluated by deterministic and stochastic sensitivity analyses. Following the World Health Organization's guidelines, we will define the willingness-to-pay (WTP) threshold as 1 to 3 times the local gross domestic product per capita. Interventions with an ICER below the threshold will be considered cost-effective. We will also compare the total dollar amount spent on implementing this program against the cost savings, if any, attributable to the interventions (CDS-OS + CDS-MTDM) to calculate the corresponding ROI.

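### The CDS regressions name no small-sample method for clustered standard errors although CDS-MTDM has only about 10 to 16 clinicians, and the primary model omits the factors that stratified randomization.

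*Combined protocol and SAP*

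**What the plan says.** **Randomization (section 6.2).** Clinicians were split into HF specialists and others. Both groups were stratified by MTDM referral history (none, or 1 to 100%). Non-HF specialists were also stratified by role (three levels) and region (three levels). The stated reason is prognostic: "Randomization was stratified as described below given concerns about imbalances in GDMT prescribing practices across clinics, certain roles, and current MTDM referral practices". There were 155 allocations, 103 for clinicians in post and 52 for possible newcomers, split 45/45/10. For newcomers, "all new clinicians were assigned to the 0% MTDM referral history stratum".

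**Primary CDS model (section 7.2.2).** "Regressions will include as covariates education arm and interactions between CDS and education". These terms are then selected by significance: "We will retain both terms if the interaction is significant and retain the main effect if only it is significant". The final model may therefore hold no baseline covariate. Anything else is exploratory: "covariates will be added to exploratory versions of the final models as sensitivity analyses". The purpose and examples given are "to adjust for measured differences across clinicians, such as role, number of patients seen, and baseline rates of prescribing each of the GDMT classes". Role is among the examples; HF-specialist status, referral history and region are not.

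**Standard errors (section 7.2.3).** OLS with "heteroskedasticity-robust standard errors clustered at the clinician level (to account for clustering of patients within clinicians". No finite-sample variant or degrees-of-freedom rule is given there or in section 7.1.

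**The concern.** There are two linked gaps.

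First, cluster-robust standard errors rely on many clusters on each side of a contrast. The trial has 103 or more clinicians in all, but the CDS-MTDM contrast depends on the 10 to 16 in that arm. Ordinary versions of the estimator tend to be too small there, and a normal reference (or a t reference on total clusters minus one) ignores how few degrees of freedom the contrast has. One of the two main hypotheses could then be tested at well above 5%.

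Second, the sponsor stratified on factors it believed were related to prescribing, and the primary outcome is a prescribing change. Leaving them out may waste precision. Stratifying does not make adjustment redundant here, because with few clinicians per stratum the arms are probably only partly balanced within strata.

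**Working it through.** **1. The plan's own power figures.** Section 7.1 gives 80% power for about 5 points (CDS-OS) and 9 points (CDS-MTDM) with 4,300 patients. It gives no control rate or intracluster correlation (ICC), so the figures cannot be reproduced exactly, only solved backwards.

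- Patients at 45/45/10: 1,935 / 1,935 / 430.
- Standard error implied by 5 points: 5 / 2.8016 = 1.785 points.
- At an assumed control rate of 30%, the unclustered variance is (0.30×0.70 + 0.35×0.65)/1,935 = 0.000226. The design effect is 0.01785² / 0.000226 = 1.41.
- With equal clinician sizes, ICC = 0.41/(m − 1). With 103 clinicians m = 41.7 and ICC = 0.010; with 155, m = 27.7 and ICC = 0.015.
- For control rates from 50% down to 10%, the ICC runs from 0.006 to 0.045 (103 clinicians) or from 0.009 to about 0.07 (155).

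The 5-point figure is therefore plausible. An ICC of 0.012 is compatible with it at a 30% control rate; 0.05 fits only if the control rate is near 10%.

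The allocation alone gives a standard error ratio of sqrt[(1/1,935 + 1/430)/(2/1,935)] = 1.66, hence 5 × 1.66 = 8.3 points for CDS-MTDM against the stated 9.

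**2. Strata and arm size.** Strata: 3 roles × 3 regions × 2 referral levels + 2 for HF specialists = 20. Clinicians per stratum: 103/20 = 5.2 to 155/20 = 7.8. The smallest block giving exactly 45/45/10 is 20 (9:9:2); the block size is not stated. CDS-MTDM clinicians: 10.3 to 15.5.

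**3. Type I error for CDS-MTDM.** Two simulations used 9:9:2 blocks within 20 strata. Strata explained 0, 25 or 50% of between-clinician variance (an assumption), and models were fitted with and without six strata main-effect terms.

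| Setting | Unadjusted | Main effects added |
|---|---|---|
| CR1 with 1.96; control rate 20 to 40%; 103 or 155 clinicians; equal or unequal sizes | 5.6–11.8% | 6.7–12.2% |
| CR1 with t on clusters minus one; 30%; ICC 0.012 or 0.05; 103 clinicians | 8–11% | 9–12% |
| The same, 155 clinicians | 7–9% | 7–9% |

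With CR2 and Satterthwaite degrees of freedom, type I error was 3.9 to 5.7% in the first simulation and 3.5 to 6.1% in the second. With 20 stratum indicators, the ordinary method gave 10 to 14% with 103 clinicians. For CDS-OS with 103 clinicians, the ordinary method gave 5 to 7% unadjusted and 7 to 8% with main effects.

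**4. Precision from adding main effects** (30%, ICC 0.012, clinician sizes varying with CV about 0.7). The standard deviation of the estimate, in both comparisons, is 0 to 4% worse if strata explain nothing, 0 to 3% better at a quarter, and about 3 to 8% better at a half. At ICC 0.05 the gain is about 4 to 8% at a quarter and 10 to 18% at a half.

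**5. Power with CR2 and Satterthwaite degrees of freedom** (same inputs as step 4, ICC 0.012), without → with main effects:

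| Strata share | Clinicians | CDS-OS, 5 points | CDS-MTDM, 9 points |
|---|---|---|---|
| 0 | 103 | 0.70 → 0.68 | 0.68 → 0.67 |
| 25% | 103 | 0.71 → 0.72 | 0.66 → 0.70 |
| 50% | 103 | 0.72 → 0.78 | 0.69 → 0.76 |
| 0 | 155 | 0.77 → 0.76 | 0.79 → 0.78 |
| 25% | 155 | 0.78 → 0.79 | 0.77 → 0.79 |
| 50% | 155 | 0.78 → 0.82 | 0.78 → 0.83 |

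For CDS-MTDM with 103 clinicians, uncorrected power looks like 0.79 to 0.82, but that is bought with excess type I error. The simulated sizes are unequal, whereas the back-solved ICC assumes equal sizes, so these powers are not a test of section 7.1.

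**6. Patient baseline GDMT.** From the usage rates in section 4, assuming independence, the variance of the class count is 0.557 to 0.625. With assumed slopes of 5 or 10 points per class, the share of patient-level variance explained is 0.05² × 0.557/0.24 = 0.6% to 0.10² × 0.625/0.16 = 3.9%. That is little.

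**The case against.** **The SAP does not say it will use an uncorrected method.** This stands. The 6 to 12% applies only if an ordinary variant is used. The stated pair of 5 and 9 points is even compatible with a power analysis that used small degrees of freedom: keeping the 1.66 ratio, with 60 to 90 degrees of freedom for CDS-OS and 10 to 14 for CDS-MTDM, t-based power gives 8.8 to 9.1 points. Rounding or unequal clinician sizes could explain the 9 equally well. A reader might infer that the planned test is known to be anti-conservative; the documents support only that the variant is unspecified.

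**The precision loss is not established.** This also stands. The effect of adjustment changes sign with how prognostic the strata are, and the documents give no figure for that. The larger gains need a higher ICC than most control rates allow.

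**The plan is partly covered.** Exploratory models will include role and baseline prescribing rates, and the list of examples is open. That softens the second gap but leaves the primary estimate unadjusted.

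**Tempting readings to avoid.** Omitting the strata does not bias a randomized comparison. The ratio 9/5 should not be read as the ratio of the two standard errors, since the allocation implies 1.66. Nor is the unadjusted CDS-OS test shown to be conservative: simulated type I error with 103 clinicians was 5 to 7%.

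**Conclusion.** The point holds as one of specification and efficiency. The more important half is the unnamed small-sample method: with about 10 to 16 CDS-MTDM clinicians, the choice moves type I error between about 5% and roughly 6 to 12%. The omitted strata are the lesser half: adjustment changes the standard deviation by about +4% to −8% at ICC 0.012, and gains more only if both the ICC and the strata effects are larger. The halves are linked because adjusting without the correction tends to raise type I error, most clearly for CDS-OS and with full stratum indicators. All sizes rest on assumed control rate, ICC, block size, strata effects and clinician sizes. Confidence is high on what the text omits and medium on the magnitudes.

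**What to change.** Amend sections 7.2.2 and 7.2.3 before outcomes are compared by arm:

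1. Specify CR2 standard errors with Satterthwaite degrees of freedom, or an equivalent small-sample correction, for all CDS contrasts.
2. Include in the primary CDS model, whatever their p-values, main effects for HF-specialist status, MTDM referral history, and role and region among non-HF specialists (six terms). Code them as used at randomization, with new clinicians in the 0% referral stratum. Do not use 20 stratum indicators: with 103 clinicians and non-prognostic strata they cost about 10% in standard deviation.
3. Keep the model without these terms as a sensitivity analysis, beside the planned exploratory models.

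Patient baseline GDMT is optional.

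**Cost.** SAP wording only; the strata data already exist. Section 10 reports that control and CDS prescribing had not been compared, so as of this version pre-specification was still possible. CDS-MTDM intervals will be wider and its power lower but honest. There is a slight variance penalty if the strata are not prognostic. Region will overlap with the site-assigned education term, and new-clinician status with its 'other' level, so the SAP should state that all these terms are kept together.
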